## Sensitivity #1

A sensitivity analysis will be performed to assess the robustness of the primary analysis based on MMRM. Intermittent missing values will first be imputed using the Markov Chain Monte Carlo (MCMC) method which assumes a joint multivariate normal model for variables in the imputation model. Then a control-based pattern imputation is applied to the monotone missing data under the assumption of data missing not at random (MNAR). PROC MI using the MCMC statement will be used to implement the first step. Then PROC MI using the MONOTONE and MNAR statements will be used to create the complete data sets. MNAR will be imputed using Copy Reference method and number of imputations will be 30. The same MMRM analysis as defined for the primary analysis will be performed on the complete data sets, and the results will be combined using PROC MIANALYZE. This analysis will be performed on the mITT population.

#### Sensitivity #2

Primary endpoint will be analysed using the observed cases (no imputations) using an analysis of covariance (ANCOVA) model including treatment as fixed factor and baseline score as covariate. Results for the outcome of the primary endpoint will be presented for the least square means estimates and 95% CIs. This analysis will be performed on the mITT population.

## Sensitivity #3

Primary efficacy analysis will be repeated for the PP Population.

## Sensitivity #4

The primary efficacy analysis will be repeated using data without imputation for the visits of discontinued patients for the mITT population.

Subgroup analysis as defined in section 3.6 will be performed for the primary endpoint across all predefined groups, with a particular focus on comparing patients taking neuroleptics as concomitant medication during the study versus patients not taking neuroleptics during the study. For this subgroup, descriptive statistics for the TMC score and changes

Statistical Analysis Plan	Version 1.0		Page 20 of 37
Sponsor	SOM Biotech	Protocol No	SOMCT03

from baseline by treatment group and by visit (including V6) will be presented, as well as time profiles of the mean TMC scores with standard error of the mean (SEM) will be provided.

For the subgroup analysis assessing patients with correct versus incorrect down titration phase between V5 and V6, only descriptive statistics for TMC score on visits will be repeated on the mITT to show the evolution of the TMC score between V5 and V6 after IMP interruption.

## 4.7.2 Secondary endpoints

## **Key secondary endpoint:**

• CGI change (CGI-C) at V5 (end of maintenance)

The key secondary efficacy endpoint will be analysed for the mITT and PP Population.

To preserve the family-wise error rate at the 0.05 level when comparing the two doses of SOM3355 versus placebo and comparing a primary endpoint and key secondary endpoint, statistical testing will be carried out using the Holm procedure for CGI-C if the primary endpoint is significant for both doses. The smallest p-value of the two comparisons will be first compared at the two-sided 0.025 level and if statistically significant, the other p-value will be compared at the two-sided 0.05 level.

## Other secondary endpoints:

They will be assessed in the following order:

- TMC-response defined as improvement  $\geq 2$  in TMC score between the baseline and the end of maintenance dose
- The percentage of change in TMC score
- The PGI change
- Total Motor Score (TMS) of the motor part of UHDRS®
- Gait sub-score of the motor part of UHDRS®
- Dystonia sub-score of the motor part of UHDRS®
- EQ-5D-5L measuring quality of life

Secondary efficacy endpoints will be analysed for the mITT Population.

The type I error will be set at 0.05 (two-sided) and the coverage level of confidence intervals to 95% for all secondary efficacy analyses. No multiplicity adjustment will be applied for the statistical inferences of the secondary efficacy endpoints.

## 4.7.2.1 Clinical Global Impression

The CGI-Severity (CGI-S) assessed at baseline is a 7-point Likert Scale that asks the clinicians to rate, considering their total experience with this type of patients, the level of illness due to chorea on the illness severity ranging from normal (1) to extremely ill (7) (CGI-Severity).

Statistical Analysis Plan	Version 1.0		Page 21 of 37
Sponsor	SOM Biotech	Protocol No	SOMCT03

Then, after therapy initiation, the CGI-Change (CGI-C) asks the clinician to assess the overall global change in the choreic symptoms since the start of study drug dosing, in a 7-point Likert Scale ranging from very much worse (7) to very much improved (1).

CGI-S will be assessed at the inclusion (Visit 1 at Day 0), and CGI-C at each following visit (from V2 to V6). For the CGI-C, patients with a score of 1 (very much improved), 2 (much improved) or 3 (minimally improved) will be defined as "Improved" and patients with a score of 4 (No change), 5 (Minimally worse), 6 (Much worse) and 7 (Very much worse) will be defined as "Not improved".

CGI-S (baseline characteristic) and CGI-C results will be analysed descriptively at each visit.

A logistic regression model will be performed for CGI-C at V5 (end of maintenance dose) including the treatment group as the main factor in the model. Estimates along with 95% confidence intervals for the difference in response proportion and the odds ratio of response will be derived from this model.

In addition, histogram will be presented.

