## 4.1.2 Missing data

In case of premature discontinuation, values collected at the end of study visit (EOS) or Unscheduled Visit (if it is the last visit) will be imputed to the first missing visit of the patients. For example, a patient withdrew between V3 and V4 (i.e. V4 is missing), then the value recorded at EOS will be imputed to V4. If a patient discontinues exactly at the time of a visit, but the value is recorded in the EOS page, this value will be imputed to the visit when the discontinuation occurred.

Partial dates are allowed on the eCRF for adverse event (AE) onset and resolution dates, concomitant medication start and stop dates, and concomitant procedure dates. An entry for the year is required in the eCRF system for each of these dates. Only the month and day may be entered as unknown. Dates from these forms will be reported in listings as collected. Every effort will be made to query missing dates particularly to clarify the onset day and time of AE occurring at visit 1 to determine if the AE is treatment emergent or not.

For records with missing AE onset date, the following procedure will be employed for use in determining whether the AE is treatment emergent:

- AE onset dates with missing day and non-missing month will be assumed to occur on the first day of the non-missing month, except for AEs occurring in the first month of dosing, in which case the date will be set to the first day of dosing.
- AE onset dates with missing month will be assumed to occur on the first day of the non-missing year (i.e., January 1), except for AEs occurring in the first year of dosing, in which case the date will be the first day of dosing.

For records with a missing medication start and/or stop date, the following procedure will be employed for use in determining whether the medication is prior or concomitant:

- Medication start dates with a missing day and non-missing month will be assumed
  to occur on the first day of the non-missing month, except for medications occurring in the first month of dosing, in which case the date will be the first day of
  dosing.
- Medication start dates with missing month will be assumed to occur on the first day of the non-missing year (i.e., January 1), except for medications occurring in the first year of dosing, in which case the date will be the first day of dosing.

Statistical Analysis Plan	Version 1.0		Page 14 of 37
Sponsor	SOM Biotech	Protocol No	SOMCT03

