## 4.7.2.2 Percentage of responders on TMC score

TMC score is assessed at each visit from V0 to V6.

V0 and V1 values are used to calculate the baseline (mean of the 2 values), and V4 V5 values for the end of maintenance dose.

Assessment at V6 occurs after the drug interruption with one week at 200 mg OD and the last week under placebo.

TMC score evolution will be assessed at each visit.

The number and percentage of responders with an improvement of at least 2 points in the TMC score will be calculated in each treatment group at each visit.

The TMC response status ("Responder" vs. "Not responder") will be described at each visit.

Logistic regression model will be performed for responders on TMC score at V5 (end of maintenance dose) including the treatment group as the main factor in the model. Estimates along with 95% confidence intervals for the difference in response proportion and the odds ratio of response will be derived from this model.

In addition, histogram will be presented.

This analysis will be repeated on the PP population.

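### The key secondary CGI-C test at V5 loses mITT patients who stop before V4, and no classification rule or sensitivity analysis covers them

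*SAP*

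**What the plan says.** **Status of CGI-C.** SAP 2.2 and 4.7.2 bring CGI-C into the family-wise error control: "statistical testing will be carried out using the Holm procedure for CGI-C if the primary endpoint is significant for both doses". Within that step, "The smallest p-value of the two comparisons will be first compared at the two-sided 0.025 level", and the other p-value is then tested at 0.05. The remaining secondary endpoints, including PGI-C and TMC response, get no multiplicity adjustment.

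**Model.** SAP 4.7.2.1: "A logistic regression model will be performed for CGI-C at V5 (end of maintenance dose". Treatment is the only factor it names. Scores 1 to 3 count as *Improved* and 4 to 7 as *Not improved*. A missing score has no category. Protocol 9.4.2 also names logistic regression for categorical endpoints and is equally silent on missing scores.

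**Population.** "The key secondary efficacy endpoint will be analysed for the mITT and PP Population". Membership of mITT needs one dose and one post-baseline TMC score (SAP 3.4).

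**Missing data.** The only visit-level rule is in SAP 4.1.2. After premature discontinuation, the end-of-study value (or a last unscheduled one) "will be imputed to the first missing visit of the patients". In the SAP's own example, a stop between V3 and V4 fills V4.

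**The primary endpoint, by contrast.** SAP 4.7.1 gives TMC an estimand, an MMRM under MAR, a fallback to V4 when V5 is missing, and Sensitivity #1 to #4. None of these is extended to CGI-C.

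**Related endpoints.** PGI-C (SAP 4.7.2.4) has the same V5 logistic model. For TMC response, SAP 4.7.2.2 says "Logistic regression model will be performed for responders on TMC score at V5 (end of maintenance dose", yet the same section and SAP 6.1 define the outcome at end of maintenance, which is built from V4 and V5.

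**The concern.** A single-visit logistic model has no mechanism for using a patient's earlier visits, whereas the MMRM does. Read together, SAP 4.1.2 and 4.7.2.1 turn a nominal mITT analysis into one restricted to patients who reached V5 or stopped just before it.

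The information lost has often been collected. CGI-C is scored at every visit from V2. Protocol 5.7 also asks early stoppers to undergo the end-of-treatment assessments whenever possible, but the first-missing-visit rule files that score at V2, V3 or V4, where the V5 model cannot see it.

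The direction of any bias depends on who leaves. Protocol 5.7 lists severe or orthostatic hypotension and untolerated bradycardia among the reasons for withdrawal, and Protocol 2.2 describes bradycardia and hypotension as known effects of the drug. If such stops are more frequent on active drug and those patients would not have been rated improved, the patients left in the active arms are a favourable selection.

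**Working it through.** **1. Who has a V5 score under SAP 4.1.2**

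| Patient stops | Visit that receives the end-of-study score | V5 CGI-C |
|---|---|---|
| before V2 | V2 | missing |
| between V2 and V3 | V3 | missing |
| between V3 and V4 | V4 | missing |
| between V4 and V5 | V5 | present |

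A patient in any of the first three rows with a post-baseline TMC score is in mITT but not in the V5 model.

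**2. How many**

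The plan enrols 43 per arm (129 in all) and allows 10% dropout (SAP 1.4). Expected stoppers: 0.10 × 129 = 12.9, or 4.3 per arm. Assume stops are spread evenly over the 70 days to V5. The share between V4 (day 63) and V5 (day 70) is 7/70 = 10%, or 1.3 patients. The other 12.9 − 1.3 = 11.6 would have no V5 CGI-C. Those without any post-baseline TMC are outside mITT anyway.

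**3. Size of the selection effect**

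The documents give no CGI-C response rate and no dropout by arm, so these are assumptions: 40% improved in both arms when every stopper counts as not improved, and dropout of 5% on placebo and 15% on active drug.

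Completer rate = composite rate / (1 − dropout):
- placebo: 0.40 / 0.95 = 42.1%
- active: 0.40 / 0.85 = 47.1%
- spurious difference: 5.0 points

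**4. False-claim rate for one dose comparison**

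Simulation with 43 per arm and a Wald test on the log odds ratio:

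z = [ln(a/b) − ln(c/d)] / √(1/a + 1/b + 1/c + 1/d)

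Here a and b are improved and not improved on active drug, and c and d the same on placebo. A claim for the drug needs z > 2.241, which is the favourable half of two-sided 0.025 (nominal 1.25%). The gate on the primary endpoint is not applied.

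| Dropout, placebo / active | V5 completers only | Stoppers counted as not improved |
|---|---|---|
| 10% / 10% | 1.2% | 1.1% |
| 5% / 15% | 3.4% | 1.1% |
| 3% / 20% | 6.7% | 1.1% |

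An exact binomial calculation with a pooled two-proportion test, fixing the completers at 41 and 37, agrees. At 5% / 15% it gives 3.1%, 3.3% and 4.6% in the drug's favour for composite rates of 30%, 40% and 50%.

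**5. The same check under a different null**

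Now let the response each patient would have had at V5 be 40% in both arms and unrelated to dropout.

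| Dropout, placebo / active | Completers: false claim for drug | Stoppers not improved: false claim for drug | Stoppers not improved: false claim for placebo |
|---|---|---|---|
| 5% / 15% | 1.2% | 0.4% | about 3% |
| 3% / 20% | 1.2% | 0.2% | about 5% |

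**6. Power cost of counting stoppers as not improved**

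Assume true response of 40% on placebo and 70% on active drug, unrelated to dropout. Power at two-sided 0.025 falls from 66% to 39% with 5% / 15% dropout, and from 66% to 60% with 10% / 10%.

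**The case against.** Several points on the other side stand.

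- **The SAP does not say that patients are dropped.** Omission is what software does where the text is silent. That is correct, but the first-missing-visit rule is explicit and leaves V5 empty, so the silence has a predictable result.
- **Not every early stopper is lost.** A stop between V4 and V5, or at V5, keeps a V5 score. On the even-spread assumption this rescues about one stopper in ten.
- **The inflation depends on the estimand.** The 3.4% arises only when the null is equal composite response with stoppers not improved. The one strategy the SAP states for study discontinuation, on the primary endpoint, is hypothetical under MAR. If dropout is unrelated to response, the completer analysis holds its level, and counting stoppers as not improved is the distorted method.
- **The test is gated.** CGI-C is reached only if both doses succeed on TMC. The gate can only lower the probability of a false CGI-C claim, so the ungated figures are not the error rate of the protected claim.
- **Unequal dropout is assumed.** The plan allows a single 10%. Protocol 2.2.1 reports that the most frequent adverse events in the earlier HD trial did not lead to withdrawal, although that trial went no higher than 400 mg/day.

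A reader might also infer that PGI-C and TMC response share the defect inside the protected family. The documents do not support this. Both lie outside that family. TMC response has a V4/V5 end-of-maintenance definition with a fallback, so its problem is conflicting wording and not a clear completer rule.

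**Conclusion.** The gap is real for CGI-C. Followed as written, the SAP excludes mITT patients who stop before V4 from the only secondary test under error control, leaves their earlier scores unused, and offers no analysis that would show whether this matters. The PP repeat does not help, because the PP population is defined by completing the study.

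At the planned 10% dropout with evenly spread stops, about 11.6 of 129 patients would lack a V5 score. The bias favours the drug only if dropout is higher on active drug and stoppers would not have improved. On the assumed 5% / 15% dropout and 40% composite rate, the ungated one-comparison false-claim rate is about 3.4% instead of 1.1%.

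A reader might infer that the trial's type I error is inflated. The documents do not support that: equal dropout, or dropout unrelated to response, gives no inflation. The defect is an unspecified estimand and an unexamined missing-data assumption in a protected test, and it should be corrected before unblinding.

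**What to change.** 1. In SAP 4.7.2.1, state the intercurrent-event strategy for discontinuation and how an mITT patient without a V5 CGI-C is handled.
2. Keep all mITT patients in the V5 analysis. One way consistent with the primary's hypothetical strategy is multiple imputation under MAR from the observed V2 to V4 and end-of-study CGI-C scores, followed by the planned logistic model.
3. Add a composite analysis that counts patients without a V5 score as *Not improved*. It can be a sensitivity analysis, or the main analysis if the sponsor chooses that estimand. The choice should be explicit, because the composite loses power when dropout is higher on active drug.
4. Apply the same handling to PGI-C, noting that it is outside the error-controlled family.
5. For TMC response, reconcile the V5 wording of the model in SAP 4.7.2.2 with the V4/V5 end-of-maintenance definition in SAP 4.7.1, 4.7.2.2 and 6.1.

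The cost is SAP wording and one or two extra analyses, with no new data collection.

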## 4.7.2.2 Percentage of responders on TMC score

TMC score is assessed at each visit from V0 to V6.

V0 and V1 values are used to calculate the baseline (mean of the 2 values), and V4 V5 values for the end of maintenance dose.

Assessment at V6 occurs after the drug interruption with one week at 200 mg OD and the last week under placebo.

TMC score evolution will be assessed at each visit.

The number and percentage of responders with an improvement of at least 2 points in the TMC score will be calculated in each treatment group at each visit.

The TMC response status ("Responder" vs. "Not responder") will be described at each visit.

Logistic regression model will be performed for responders on TMC score at V5 (end of maintenance dose) including the treatment group as the main factor in the model. Estimates along with 95% confidence intervals for the difference in response proportion and the odds ratio of response will be derived from this model.

In addition, histogram will be presented.

This analysis will be repeated on the PP population.

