# 9.4.1. Primary Efficacy Endpoint

The primary efficacy endpoint for this study is the change in Total Maximal Chorea (TMC) score from baseline (defined for each patient as the average of values at the screening visit (Visit 0) and the inclusion visit (Visit 1)) to the end of maintenance therapy (defined for each patient as the average of values from the end of Week 9 (Visit 4) and the end of Week 10 (Visit 5)).

Primary efficacy analyses will be based on the modified intent-to-treat (mITT) Population.

The estimand of the primary efficacy analysis is defined according to ICH-E9-R1. The estimand reflects a mixed strategy for the inter-current events as presented in the table below.

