## 9.4.2. Secondary Efficacy Endpoints

The secondary endpoints will be assessed hierarchically in the following order:

- The CGI change between the baseline and the end of maintenance dose
- TMC-response defined as improvement ≥ 2 in TMC score between the baseline and the end of maintenance dose in each group
- The percentage of change in TMC score
- The PGI change between the baseline and the end of maintenance dose
- Total Motor Score (TMS) of the UHDRS®
- Gait sub-score of the UHDRS®
- Dystonia sub-score of the UHDRS®
- EQ-5D-5L measuring quality of life

Secondary efficacy endpoints will be analyzed using the mITT Population.

For continuous efficacy endpoints with longitudinal data, the same MMRM model, as described for the primary endpoint will be performed. For other continuous efficacy endpoint measured at baseline and end of maintenance dose, an ANCOVA model will be used.

Categorical efficacy endpoints will be analyzed using a logistic regression model.

The type I error will be set at 0.05 (two-sided) and the coverage level of confidence intervals to 95% for all secondary efficacy analyses. No multiplicity adjustment will be applied for the statistical inferences of the secondary efficacy endpoints.

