## 3.6 Subgroup analyses

Subgroup analyses of the primary efficacy (change in Total Maximal Chorea (TMC) score from baseline to the end of maintenance therapy at V5) are planned for the following subgroups:

- patients not taking neuroleptics during the study vs patients taking neuroleptics as concomitant medication during the study
- gender: male, female
- age: < median,  $\ge$  median
- country: France, Spain, UK, Poland, Italy, Germany
- baseline TMC: < median, ≥ median
- baseline TMS: < median, > median

This analysis will be performed on the mITT population, except the neuroleptics subgroup, which will also be repeated on the PP population.

Additional subgroup, correct versus incorrect down titration phase between Visit 5 and Visit 6, is defined as:

- patients who have performed a correct down titration phase i.e. who correctly took the IMP at half dose (1 capsule/ day) for a week and then capsules from placebo bottle for at least 4 days.
- patients who did incorrect down titration
  - o who took 2 capsules/day of IMP so remaining at full dose with no down titration, and then placebo with abrupt IMP discontinuation
  - o or who took the IMP at half dose (1 capsule/ day) for 2 weeks with no placebo wash out or less than 4 days under placebo

For this subgroup, only descriptive statistics on visits for the TMC score will be repeated on the mITT population to show the evolution of the TMC score between V5 and V6 after IMP interruption. In addition, time profiles of the mean TMC scores with standard error of the mean (SEM) will be presented.

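### The TMC responder model in SAP 4.7.2.2 is set at V5, but the protocol measures TMC response to the mean of V4 and V5, and the change is not declared

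*SAP*

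**What the plan says.** Protocol 9.4.2 lists the endpoint as "TMC-response defined as improvement ≥ 2 in TMC score between the baseline and the end of maintenance dose". Protocol 9.4.1 fixes the end of maintenance for TMC, patient by patient, as "the average of values from the end of Week 9 (Visit 4) and the end of Week 10 (Visit 5"; the synopsis and section 3.2 give the same two-visit mean.

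The SAP mostly follows this. Section 4.7.1 repeats the average for the primary endpoint and adds that if one of V4 and V5 is missing, the other is used. Section 4.7.2.3 uses the average for percentage change in TMC. The list of other secondary endpoints in section 4.7.2 keeps the protocol's definition of response.

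Section 4.7.2.2 is where the text divides. It opens with "V0 and V1 values are used to calculate the baseline (mean of the 2 values), and V4 V5 values for the end of maintenance dose". It then asks for response to be described at each visit, and specifies the inferential analysis as "Logistic regression model will be performed for responders on TMC score at V5 (end of maintenance dose". It does not say what happens when V5 is missing.

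Section 6.1 defines TMC improvement to the end of maintenance without naming a visit. Section 2.2, which lists departures from the protocol, contains only the multiplicity change for CGI-C.

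**The concern.** Response at a cut of 2 points is how the mean TMC result will be put into clinical terms. It is a named secondary objective and stands first among the other secondary endpoints. A reader will expect it to describe the same quantity as the primary analysis. If the model is fitted at V5, it does not: the end-of-treatment value comes from one rating instead of two, and patients near the cut can land on the other side.

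Three things are at stake. The tested endpoint would differ from the protocol's without being declared. The single-visit value is at least as variable as the two-visit mean when the two visits have equal variance, so some power is lost. And the patients contributing to the responder model need not be those contributing to the primary analysis.

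**Working it through.** **1. The texts side by side.**

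| Place | End-of-maintenance value for TMC |
|---|---|
| Protocol synopsis, 3.2, 9.4.1 | mean of V4 and V5 |
| Protocol 9.4.2 (response) | end of maintenance, no visit named |
| SAP 4.7.1 (primary) | mean of V4 and V5; the other visit if one is missing |
| SAP 4.7.2.3 (percentage change) | mean of V4 and V5; the available one if one is missing |
| SAP 4.7.2.2, opening | V4 and V5 values |
| SAP 4.7.2.2, logistic model | V5 |
| SAP 6.1 (TMC improvement) | end of maintenance, no visit named |

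The logistic-model line is the only one of these that names V5 by itself.

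**2. Complete data, one patient.** Baseline (mean of V0 and V1) 14, V4 = 10, V5 = 13.
- To the mean: (10 + 13)/2 - 14 = 11.5 - 14 = -2.5, a responder.
- To V5: 13 - 14 = -1, not a responder.

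**3. Incomplete data.** SAP 4.1.2 places the end-of-study value of a patient who discontinues into the first missing visit; its own example is a withdrawal between V3 and V4, with the value put into V4. Under SAP 4.7.1 that patient has a primary-endpoint value, taken from V4. At V5 the patient has nothing, and SAP 4.7.2.2 gives no fallback.

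**4. The plan's own figure.** The documents give no responder rate and no power for this endpoint. Their sample size supplies the SD, the effect and n. With a difference of -2.5, SD 3.5 and two-sided alpha 0.025, the noncentral t power is 79.4% at 38 per arm and 80.5% at 39, so the stated 39 is reproduced.

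**5. Size of the effect.** From the documents: SD 3.5, read as the SD of the change to the V4/V5 mean; active minus placebo -2.5; cut at -2; 39 per arm. Assumed: independent rating error with SD s = 1 to 2 points at each visit, and a mean placebo change of -1 (so -3.5 on active).

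Replacing the mean of two ratings by one raises the error variance from s²/2 to s², so SD at V5 = √(3.5² + s²/2). The response rate for mean change μ is Φ((-2 - μ)/SD).

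| | SD of change | Placebo | Active | Difference |
|---|---|---|---|---|
| V4/V5 mean | 3.50 | 38.8% | 66.6% | 27.8 points |
| V5, s = 1 | √12.75 = 3.57 | 39.0% | 66.3% | 27.3 points |
| V5, s = 2 | √14.25 = 3.77 | 39.6% | 65.4% | 25.9 points |

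The difference shrinks by 0.5 point at s = 1 and 1.9 points at s = 2. With placebo changes of 0 and -2 as well, the range is 0.4 to 1.9 points. Approximate power at two-sided 0.05 falls from 69.9% to 68.2% (s = 1) or 63.4% (s = 2).

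**6. Check with whole-number scores.** A simulation of 1,000,000 patients per setting (integer ratings, true baseline mean 14, mean changes from 0 to -3.5) gives 5.6% to 6.2% of patients changing status at s = 1, and 10.8% to 11.9% at s = 2. At s = 2 with the means above, response is 41.6% and 69.1% on the V4/V5 mean (27.5 points) and 42.2% and 67.8% at V5 (25.6 points). The moves go both ways: on placebo at s = 2, about 5.6% lose response and 6.3% gain it.

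**The case against.** The strongest reply is that V5 is only a label for the averaged time point. The word alone does not appear. SAP 4.2 describes completion of V5 as the primary endpoint assessment. SAP 3.6 describes the primary variable as the change in TMC "score from baseline to the end of maintenance therapy at V5", although SAP 4.7.1 defines it on the average. The primary SAS code carries nine treatment-by-visit coefficients, that is 3 arms × 3 time points, which fits V2, V3 and one combined end-of-maintenance point.

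This stands as a possible reading, so an intended switch of endpoint is not established. It does not remove the point. The same phrase about V5 is used in SAP 4.7.2.1 and 4.7.2.4 for CGI-C and PGI-C, where it means a single visit, and section 4.7.2.2 itself works visit by visit. Two programmers could derive different endpoints from it.

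Two stronger readings are tempting. A reader might infer that section 4.7.2.2 itself defines the end of maintenance as the average and then contradicts itself. It says only "and V4 V5 values for the end of maintenance dose", and in that sentence the mean is attached to V0 and V1; the explicit average is elsewhere. A reader might also infer from SAP 3.6 that the subgroup analyses use a second altered endpoint. That section names the primary efficacy variable, so shorthand is the better reading.

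It is also fair to say that the effect is small. At s = 2 the loss of 1.9 points is 0.019 × 39 = 0.7 of a patient per arm, against a standard error of √(0.416 × 0.584/39 + 0.691 × 0.309/39) = 10.8 points for the difference. If V4 and V5 correlate highly, it is smaller still.

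**Conclusion.** The point holds as an undeclared inconsistency that should be corrected. On its plain reading, SAP 4.7.2.2 tests response at one visit where the protocol calls for the mean of two. The misclassification in the worked patient and the gap for a patient with V4 only follow from the text and need no assumption.

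The size does rest on an assumption, because neither document gives a visit-to-visit rating SD. At 1 to 2 points, about 6% to 12% of patients change status, mostly cancelling; the responder difference falls by about 0.5 to 2 points, and power by about 2 to 6 points.

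A reader might infer that the trial's main conclusion is at risk. It is not: this is a secondary endpoint tested without multiplicity adjustment, and the primary test, its Holm procedure and the sample size do not depend on it. Nor is the two-visit design abandoned, since the V0/V1 mean baseline is kept under either reading.

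**What to change.** In SAP 4.7.2.2, state that the logistic model uses response defined as a change of -2 or lower from the V0/V1 mean to the V4/V5 mean, and that the SAP 4.7.1 rule for a single missing visit applies. Keep response at V5 in the by-visit descriptive table. Carry the same sign convention into SAP 6.1, which now writes the cut as at or above -2.

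As a wording clean-up only, replace the reference to V5 in SAP 3.6 with the V4/V5 average.

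If a V5 model is what the sponsor wants, declaring and justifying it in SAP 2.2, with a rule for missing V5, would also resolve the inconsistency, though it would leave the endpoint further from the protocol.

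The cost is a few sentences in the SAP. The averaged value is already derived for the primary and percentage-change analyses, so no new data are needed.
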